11.1.5 Concomitant Medications and Procedures

The site investigator will review concomitant medications at screening, the enrollment visit, and all clinic visits, tracking start and stop dates, and dose changes on the clinical evaluation source document. Clinical research team members will track the list on a dedicated concomitant medication CRF.

Whenever a concomitant medication or study product is initiated or the dose changed, investigators should review the concomitant medications' and study products' most recent package inserts to check for the most current information on drug interactions, contraindications, and precautions.

11.1.6 Permitted Medications and Procedures

All medications and procedures are permitted that comport with inclusion and exclusion criteria.

11.1.7 Prohibited Medications and Procedures

A list of prohibited medications will be included in the MOP; patients requiring prohibited medications will not be enrolled. If use of prohibited drugs is required during treatment, study drugs will be stopped and the participant will be considered non-adherent thereafter.

11.1.8 Precautionary Medications and Procedures

Rifapentine is a strong inducer of metabolizing enzymes, so there is a risk of drug-drug interactions.

All concomitant medications, dosages, frequencies, and routes of administration will be recorded and data-entered. Site investigators will consult the list of prohibited and precautionary medications (Appendix IV) prior to starting any new medication to minimize the potential for drug-drug interactions.

11.1.9 Required Medications

Rifapentine and isoniazid as previously described

11.1.10 Rescue Medications

The first dose of rifapentine/isoniazid will be administered in the research clinic by a licensed health care professional. The clinic will be equipped with standard emergency resuscitation equipment, IV fluids, medications, and oxygen.

12. STUDY PROCEDURES/EVALUATIONS

12.1 Clinical Evaluations and Procedures

12.1.1 Screening

Obtain written informed consent or parental permission and assent *before* performing any screening procedures.

- 1. Verify study entry eligibility criteria are met
- 2. Record locator information for contacting participant throughout study
- 3. Medical history

The medical history must include all prior TB and liver disease. In addition, it must include all pre-existing and new diagnoses within 30 days prior to study entry. Allergies to any medications and their formulations must be documented. Medical history and complete physical examination, including concomitant medication history

4. Medication History

A medication history including all prescription and nonprescription medications taken within 30 days prior to study entry must be present. Include actual or estimated start and stop dates.

5. Conduct a complete physical exam

A complete physical examination at entry is to include at a minimum an examination of the skin, head, mouth, and neck; auscultation of the chest; cardiac exam; abdominal exam; examination of the lower extremities for edema.

- 6. The complete physical exam will also include signs and symptoms, diagnoses, vital signs (temperature, pulse, respiration rate, and blood pressure), height, and weight
- TB symptom screen Current cough, fever, night sweats, or unintentional weight loss, lymphadenopathy and/or other abnormalities on lung examination.
- 8. Chest X-ray (CXR) to exclude active TB disease
- 9. Persons with symptoms or signs of active TB or an abnormal chest X-ray are ineligible to participate in the study, and should be referred for investigation by health clinic staff according to local guidelines. Do not proceed with enrollment.
- Collect blood for chemistry panel including liver function tests (LFT), complete blood count (CBC), hepatitis B surface antigen (HBsAg), and interferon gamma release assay (IGRA) or TST if a documented result is not available within 90 days of screening.
- 11. HIV rapid test to confirm HIV negative status.
- 12. For individuals of childbearing potential, collect urine for βHCG.

Provide counseling and document the need for contraception and the risk of rifapentine reducing the effectiveness of oral and injectable hormonal contraception. A second barrier method should be used during the 24-week study of the patient's choice with medical advice. For those women who for some reason cannot get pregnant or who do not have sex, the use of contraceptives is not mandatory.

Screening evaluations must occur prior to the participant's starting study medications. Screening evaluations to determine eligibility must be completed within 7 days prior to study enrolment.

12.1.2 HIV Counseling and Testing

Counseling prior to and following HIV testing, and reporting HIV testing results will follow local guidelines and regulations at each site.

For study purposes, HIV-1 infection is defined as a positive result using any licensed rapid HIV test or any licensed HIV enzyme or chemiluminescence immunoassay (E/CIA) test kit. Negative study HIV testing does not require confirmatory testing. Note: the term 'licensed' refers to an FDA-approved kit or, for study sites located in countries other than the United States, a kit that has been certified or licensed by an oversight body within that country.

12.1.3 Enrollment (within 7 days of screening)

- 1. Verify that participant continues to meet study entry eligibility criteria. Update locator information for contacting participant throughout study, and collect concomitant medication history.
- 2. Repeat TB symptom screen (current cough, fever, night sweats, or unintentional weight loss). Persons with symptoms or signs suggestive of TB are ineligible to participate in the study, and should be referred for investigation by health clinic staff according to local guidelines.
- 3. For participants of childbearing potential, collect urine for β HCG, only if a result is not available from within 48 hours of enrolment.
- 4. Randomize to a treatment arm according to the study's randomization procedure.

Once randomized and enrolled, study staff will teach participants when and how to take their study regimen; including what to do if a dose is late, missed, or vomited. Participants will take their HP at home with a high fat diet to promote absorption.

Study staff will teach examples of common, local, culturally appropriate high fat foods that are available within the participant's socioeconomic status. Study staff will administer each participant's first dose with a standardized high fat meal in clinic as an example.

Participant will record her or his first dose in the medication diary with staff guidance.

5. Patient costing survey

To estimate any additional patient-level and societal costs of 1HP and 3HP (*e.g.*, ancillary healthcare visits, transportation to and from the clinic, use of formal social support programs, and costs associated with adverse events), we will randomly select 50 consenting patients in each arm of the trial to administer a patient cost survey. This patient cost survey will ask participants to record total duration of clinic visits, travel time to the clinic, and all out-of-pocket and indirect costs associated with their preventive TB treatment care/study participation through completion of treatment. Additional questions will be asked to capture information on the amount of time participants spend at home completing intervention-related activities (e.g. taking pills, completing adherence logs/diaries) and any costs associated with managing TPT-associated adverse events. The patient costing questionnaire will be integrated into existing study surveys and instruments as described in the Manual of Operations (MOP).

12.1.4 Follow-up visits

At all Visits for both treatment arms:

Targeted Physical Exam

A targeted physical examination at post-entry visits is to include vital signs (temperature, pulse, respiration rate, and blood pressure) and weight. It should be driven by any previously identified or new signs or symptoms including diagnoses that the participant has experienced since the last visit.

Signs and Symptoms

Record all signs and symptoms and grate according to the DAIDS grading criteria.

Diagnoses

Record all new diagnoses or worsening of a pre-existing condition, and grade according to the DAIDS grading criteria.

Concomitant Medications

All new concomitant medications taken since the last report and change in current concomitant medications since the last report should be recorded, including start and stop dates.

Study Treatment Modifications

Record all study drug modifications, including initial doses, participantinitiated and/or protocol-mandated modifications, inadvertent and deliberate interruptions (i.e., 3 or more missed doses) at each visit. Record permanent discontinuation of treatment.

Patient Costing Survey

The patient costing questionnaires will be administered to 50 patients who were selected at the time of enrolment to complete this survey at two time points, namely the completion of treatment and the end of the follow-up period.

Arm A: Rifapentine 600 mg daily and isoniazid 300 mg daily for 4 weeks (1HP)

Arm A will have 250 participants.

Weeks 0-4

All daily doses of rifapentine/isoniazid (HP) will be self-administered at home by the participant, except for the initial dose which will be supervised by the study staff in clinic. Participants will record their HP dose taking and doserelated food intake/time on a medication diary card (Appendix II). The research pharmacy at each site will dispense 15 or 16 rifapentine blister packs, each with 8 tablets (2 doses per pack, 30-32 doses total) and 30 or 32 300 mg INH tablets to cover the visit window period. An extra 2-4 days of medication will be provided to allow for vomited doses and to reduce the likelihood of medication dumping. Participants will be told to bring unused medication back to clinic for the 2 and 4 week visits. At enrolment, 50 participants will be selected to complete a patient costing survey and be asked to complete this survey two additional times during their follow visits (at completion of treatment and at the end of the study participation).

Week 2 (+/- 3 days) Day 14

The participant will arrive to clinic at least an hour early, so that everything is in place for drug sampling events to begin on time. Check with the participant about yesterday's HP dosing and to be sure that s/he *did not take today's HP* dose. Check to be sure s/he brought today's HP dose to clinic.

Record the exact time the sample blood and urine was collected. At any time during the events of Day 14 (Week 2 visit) (but before today's dose of HP), conduct the following assessments:

- TB symptom screen
- targeted physical exam
- adverse event assessment
- adherence questionnaire
- pill count of HP, review of medication diary card
- CBC
- chemistry panel including liver function tests
- Dried blood spot and urine collection for drug sampling
- Sampling for NAT2 gene
- urine pregnancy test for participants of childbearing potential

Week4 (+/- 3 days Day 28

The participant will arrive to clinic at least an hour early, so that everything is in place for drug sampling events to begin on time. Check with the participant about yesterday's HP dosing and to be sure that s/he *did not take today's HP* dose. Check to be sure s/he brought today's HP dose to clinic.

Record the exact time the sample blood and urine was collected. At any time during the events of Day 28 (Week 4 visit) (but before today's dose of HP), conduct the following assessments:

- TB symptom screen
- targeted physical exam

- adverse event assessment
- adherence questionnaire
- patient costing survey
- pill count of returned HP, review of medication diary card
- CBC
- chemistry panel including liver function tests
- Dried blood spot and urine collection for drug sampling
- urine pregnancy test for participants of childbearing potential

If participant is assessed to be stable on HP, s/he may take today's dose.

This is the final dose for the 1HP regimen.

Week 8 (+/- 3 days)

Study team will conduct the following assessments:

- TB symptom screen
- targeted physical exam
- adverse event assessment
- urine pregnancy test for participants of childbearing potential

Week 12 (+/- 3 days)

The study team will conduct the following assessments:

- TB symptom screen
- targeted physical exam
- adverse event assessment
- urine pregnancy test for participants of childbearing potential

Week 16 (+/- 3 days)

The study team will conduct the following assessments:

- TB symptom screen
- targeted physical exam
- adverse event assessment
- urine pregnancy test for participants of childbearing potential

Week 24 (+/- 3 days)

The study team will conduct the following assessments:

- -TB symptom screen
- targeted physical exam
- adverse event assessment
- urine pregnancy test for participants of childbearing potential
- patient costing survey

This is the final study visit
Arm B: Rifapentine 900 mg once-weekly and isoniazid 900 mg once- weekly for 12 weeks (3HP)

Arm B will have 250 participants.

Weeks 0-4

All once-weekly doses of rifapentine/isoniazid (HP) will be self-administered at home by the participant, except for the initial dose which will be supervised by the study staff in clinic. Participants will record their HP dose taking and dose-related food intake/time on a medication diary card (Appendix II).

The research pharmacy at each site will dispense 4 rifapentine blister packs, each with 8 tablets (1.33 doses per pack, 5.33 doses total) and 12 or 15 300 mg INH tablets to cover the visit window period. An extra dose of medication will be provide to allow for vomited doses and to reduce the likelihood of medication dumping. Participants will be told to bring unused medication back to clinic for the 2, 4, 8 and 12 week visits.

At enrolment, 50 participants will be selected to complete the patient costing survey and be asked to complete this same survey two additional times during their follow visits (at completion of treatment and at the end of the study participation)

Week 2 (+/- 3 days)

The study team will conduct the following assessments:

- TB symptom screen
- targeted physical exam
- adverse event assessment
- adherence questionnaire
- Pill count of HP, review of medication diary card
- CBC
- chemistry panel including liver function tests
- Urine pregnancy test for participants of childbearing potential

Week 3 (+/- 3 days for visit) Day 22 (24 hours after HP dose #4 was taken)

The participant will arrive to clinic at least an hour early, so that everything is in place for drug sampling events to begin on time.

Collect the blood and urine for drug sampling and record the exact time the sample blood and urine was collected.

The study team will conduct the following assessments:

- TB symptom screen
- targeted physical exam
- adverse event assessment
- adherence questionnaire

- pill count of returned HP, review of medication diary card

- CBC

- chemistry panel including liver function tests
- Dried blood spot and urine collection for drug sampling
- Sampling for NAT2 gene
- urine pregnancy test for participants of childbearing potential

Week 8 (+/- 3 days)

Study team will conduct the following assessments:

- TB symptom screen
- targeted physical exam
- adverse event assessment
- adherence questionnaire
- pill count of returned HP, review of medication diary card
- CBC
- chemistry panel including liver function tests
- urine pregnancy test for participants of childbearing potential

Week 12 (+/- 3 days for visit, but not for drug sampling) Day 85 (24 hours after HP dose #12 was taken)

The participant will arrive to clinic at least an hour early, so that everything is in place for drug sampling events to begin on time.

Collect the blood and urine for drug sampling and record the exact time the sample blood and urine was collected.

The study team will conduct the following assessments:

- TB symptom screen
- targeted physical exam
- adverse event assessment
- adherence questionnaire
- patient costing survey
- pill count of returned HP, review of medication diary card
- CBC
- chemistry panel including liver function tests
- Dried blood spot and urine collection for drug sampling
- urine pregnancy test for participants of childbearing potential

This is the final dose for the 3HP regimen.

Week 16 (+/- 3 days)

The study team will conduct the following assessments:

- TB symptom screen
- targeted physical exam
- adverse event assessment

- urine pregnancy test for participants of childbearing potential

Week 24 (+/- 3 days)

The study team will conduct the following assessments:

- TB symptom screen
- targeted physical exam
- adverse event assessment
- urine pregnancy test for participants of childbearing potential
- patient costing survey

This is the final study visit.

12.1.5 Treatment completion and successful treatment.

1HP

Completion of therapy is defined as having completed 28 daily doses of treatment within 6 weeks. Treatment success is defined as having taken at least 25 doses of medication confirmed by patient report and pill count, and having rifapentine or isoniazid detected in urine or DBS specimens.

3HP

Completion of therapy is defined as having completed at least 12 weekly doses of treatment within 18 weeks. Treatment success is defined as having taken at least 11 doses of medication confirmed by patient report and pill count, and having rifapentine or isoniazid detected in urine and DBS specimens.

Figure 2 shows the algorithm that will be used to classify patients as having treatment success of failure. This hierarchical approach begins with self-reported adherence, then uses pill count, and finally a composite of test results for isoniazid in urine and rifapentine and des-RPT in DBS.

Figure 2

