14.2.7 Other Toxicities

For toxicities that do not fall into one of the scenarios above, management will be as follows:

Grade 1 and 2: Participants may continue HP at the discretion of the site investigator with careful follow-up.

Grade 3 and 4: Study drugs should be held until symptoms have resolved (or until \leq Grade 2 or within normal limits). Study drugs may be permanently discontinued at the discretion of site investigator.

Site investigators are strongly encouraged to discuss discontinuations and reintroductions of study treatment with the core investigators to ensure consistency across sites.

If study drugs are suspended for any reason, participants in Arm A will have 8 weeks from enrollment to complete 28 doses of HP. Participants in Arm B will have 16 weeks from enrollment to complete at least 11 doses of HP. If the break in treatment is longer than 4 weeks, the participant will need to be rescreened for TB before recommencing HP.

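### No scheduled pill count covers permitted late dosing in either arm, and Arm B's Day 85 sampling label does not fit dose 12

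*Protocol*

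**What the plan says.** **Success and time limits.** Protocol 15.2.1 sets the dose thresholds at 25 within 8 weeks (1HP) and 11 within 16 weeks (3HP). Both need the participant's report, a pill count and a positive drug test. After a suspension, 14.2.7 says "participants in Arm A will have 8 weeks from enrollment to complete 28 doses of HP" and "Participants in Arm B will have 16 weeks from enrollment to complete at least 11 doses of HP". Protocol 12.1.5 and SAP 10.2.1 also define completion, with limits of 6 weeks (1HP) and 18 weeks (3HP). They put no time limit on success.

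**Pill counts.** Arm A participants are told to "bring unused medication back to clinic for the 2 and 4 week visits". Arm B participants are to bring theirs "back to clinic for the 2, 4, 8 and 12 week visits". The visit lists in 12.1.4 and Tables 1A and 1B show no pill count or adherence questionnaire after Week 4 in Arm A, or after Week 12 in Arm B (week 11 in Table 1B).

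**Arm B sampling day.** Section 12.1.4 places the first drug sample on Day 22, a day after dose 4. It places the second on Day 85, a day after dose 12. Table 1B puts dose 1 at week 0 and the second sample at week 11.

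**Arm A Week 4 dose.** The visit is headed Day 28 with a window of 3 days either side. The pill count comes before that day's dose. Then: "If participant is assessed to be stable on HP, s/he may take" that dose, followed by "This is the final dose for the 1HP regimen". The supply is 15 or 16 packs, "each with 8 tablets (2 doses per pack, 30-32 doses total", and "An extra 2-4 days of medication will be provided to allow for vomited doses and to reduce the likelihood of medication dumping".

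**The concern.** The protocol itself produces late finishers. New Grade 2 nausea or vomiting (14.2.1) and Grade 2 or 3 rash (14.2.2) require the drugs to be withheld, and every effort is to be made to restart them after gastrointestinal events. A participant who attends the last pill-count visit on schedule, still short because of a hold, may go on to reach the threshold inside the limit. The success definition then asks for a pill count that no later visit lists. Whether that person is scored a success would rest on self-report or an ad hoc count, in an open-label trial where this is a primary outcome.

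The Day 85 label matters because drug detection is part of the same outcome. A sample scheduled by the day number, not by the dose, would miss the period in which the drugs can be detected.

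**Working it through.** **1. The plan's own figure.** Inputs from protocol 15.4: 80% v 90%, CV k = 0.15, cluster size about 2 (m = 2), two-sided 0.05, 80% power. The CV formula for cluster-randomised proportions gives

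c = 1 + (1.960 + 0.842)² × [0.8×0.2/2 + 0.9×0.1/2 + 0.15²×(0.8² + 0.9²)] / (0.9 − 0.8)² = 124.7 clusters per arm.

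Rounded up, that is 125 clusters, or 250 people per arm, with power 80.1%. The plan's figure reproduces, and nothing below enters it.

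**2. Counts against limits.**

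| | Arm A (1HP) | Arm B (3HP) |
|---|---|---|
| Success threshold | 25 doses by Day 56 | 11 doses by Day 112 |
| Scheduled counts (weeks) | 2, 4 | 2, 3, 8, 12 (12.1.4); 2, 3, 8, 11 (Table 1B) |
| Later visits with no count (weeks) | 8, 12, 16, 24 | 16, 24 |
| Last count, window | Days 25–31 | Days 81–87 |
| Days uncovered | 56 − 31 = 25 to 56 − 25 = 31 | 112 − 87 = 25 to 112 − 81 = 31; 112 − 78 = 34 from Day 78 |

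Under the completion limits of 6 and 18 weeks, the intervals would be 42 − 31 = 11 to 42 − 25 = 17 days (Arm A) and 126 − 87 = 39 to 126 − 81 = 45 days (Arm B).

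**3. Illustrations (hold lengths assumed).**

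- *Arm A, 7-day hold, no other missed doses.* The Day 28 count shows 27 − 7 = 20 doses if dose 1 is on Day 1, or 28 − 7 = 21 if on Day 0. Even on Day 31 it shows 23 or 24. Dose 25 falls on Day 32 or 31 and dose 28 on Day 35 or 34, all well inside Day 56.
- *Arm B, three weekly doses held, dose 1 on Day 0.* A Day 78 count shows 12 − 3 = 9. A count on any of Days 81–87 shows at most 13 − 3 = 10. Dose 11 falls on Day 70 + 21 = 91 and dose 12 on Day 98, both inside Day 112.

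**4. Day 85.** With dose 1 on Day 0, dose n falls on Day 7(n − 1). Dose 4 is on Day 21, so 24 hours later is Day 22, as the protocol says. Dose 12 is on Day 77, so 24 hours later is Day 78, which matches week 11 in Table 1B. Day 85 is 85 − 77 = 8 days after dose 12, or 24 hours after a thirteenth weekly dose. Numbering from Day 1 gives Day 79, and it would also break the Day 22 label. Protocol 11.1.4 puts rifapentine detection at up to 50 hours; 8 days is 192 hours.

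**5. The Week 4 dose.** For a fully adherent participant, the visit dose is number d − d₀ + 1, where d is the visit day and d₀ the day of dose 1.

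| Visit day | 25 | 28 | 31 |
|---|---|---|---|
| Dose 1 on Day 0 | 26 | 29 | 32 |
| Dose 1 on Day 1 | 25 | 28 | 31 |

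The protocol does not fix d₀ for Arm A. Table 1A starts dosing at week 0, while 15.8.1 equates four weeks with the 28th dose, which fits Day 1. Thirty-two doses need the 16-pack supply (16 × 8 / 4 = 32), since 15 packs give 30.

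**6. What misclassification could do (assumed shares only).** Suppose a share of true successes is scored as failure for want of a count. With 125 clusters per arm:

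| Share lost, 1HP / 3HP | Success, 1HP v 3HP | Power |
|---|---|---|
| 0% / 0% | 90% v 80% | 80% |
| 2% / 0% | 88.2% v 80% | 62% |
| 5% / 5% | 85.5% v 76% | 70% |
| 0% / 5% | 90% v 76% | 97% |

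The documents give none of these shares, and the direction depends on which arm loses more.

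**The case against.** The strongest reply is that late counts are not excluded. Under 12.3.8 and 12.3.9, a visit outside its window becomes an unscheduled visit with all the procedures of the missed one, so a late Week 4 or Week 12 visit still includes a count. Section 11.1.4 describes pill counts without tying them to named visits and asks for self-reported dosing at each monitoring visit. Treatment interruptions are recorded at every visit. Product returns are recorded (11.1.3) and accountability is monitored (section 17). The SAP uses data through 24 weeks. All of this stands and narrows the gap. It does not close it, because someone who attended Week 4 or Week 12 on time while still dosing has missed no visit, and no later visit lists a count.

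A reader might also infer that the final-dose sentence tells sites to stop at 25 to 27 doses, or makes success unattainable after an early visit. The documents do not support that. The sentence sits under a Day 28 heading and agrees with the 28th dose at four weeks in 15.8.1. The wording about taking the dose is permissive. The 28-dose regimen is stated in 9.2, 11.1.1, 12.1.5 and 14.2.7, and no text makes the Week 4 count decisive for success.

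Nor do the documents show that sites will classify participants differently. Both specify a single algorithm, Figure 2, which is not reproduced in the text available and may settle whether the visit-day dose is credited.

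**Conclusion.** Two points hold. First, dosing is permitted after the last scheduled pill count in both arms, while success depends on a pill count. The interval is 25 to 31 days in each arm on the 12.1.4 windows, using the limits of 8 and 16 weeks. It affects only participants who attend on time and are still dosing; their number is not given and is probably small. Second, Day 85 is an arithmetic error for Day 78, given dose 1 on Day 0. The SAP asks for detection at least once, so an earlier positive sample could still meet the drug-test component.

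The final-dose sentence is a minor wording matter: correct on nominal Day 28 with dose 1 on Day 1 and full adherence, and incomplete otherwise.

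A reader might take the power table as evidence that the trial is underpowered or biased towards one arm. It is not: the shares are assumed, the uncovered interval on the 12.1.4 windows is the same length in both arms, and the planned 250 per arm is unaffected. The case for acting is that the gap touches a primary outcome and is cheap to close.

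**What to change.** 1. **Late count.** Add a returned-pill count and adherence questionnaire at the existing Week 8 visit for Arm A participants below 28 doses at Week 4. Do the same at the existing Week 16 visit for Arm B participants below 12 doses at their last count. For anyone still dosing, hold the visit at or after the limit (Days 56–59; Days 112–115, within the current windows). Mark both in Tables 1A and 1B and extend the instruction to bring back unused medication.
2. **Arm B sampling.** In 12.1.4, rename the Week 12, Day 85 visit to Week 11, Day 78, to match Table 1B. Changing the day alone would put sampling outside Days 81–87 and split it from the pill count.
3. **Arm A wording.** Replace the final-dose sentence with: *The final dose is dose 28; if fewer have been taken, continue at home within the permitted period.* State the day of dose 1, and that the dose taken on the Week 4 visit day counts.
4. **Limits.** Align the completion limits of 6 and 18 weeks in 12.1.5 and SAP 10.2.1 with the 8 and 16 weeks of 15.2.1. A Week 16 count would not cover dosing to Week 18.

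**Cost.** Text edits, two entries in each schedule table, and a brief count and questionnaire at one existing visit per arm for those still short. No visit is added.

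**Downside.** With dosing ended at dose 28, some late Week 4 samples fall more than 24 hours after the last dose: 48, 72 and 96 hours on Days 29, 30 and 31 (dose 1 on Day 0), or 48 and 72 hours on Days 30 and 31 (dose 1 on Day 1). Protocol 11.1.4 puts urine sensitivity at 85% at 48 hours, with 87% negative at 72 hours. Under the SAP's at-least-once rule the Week 2 sample can still suffice; protocol 15.2.1 does not carry that wording.
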